#### **Protocol Review and Amendments**

Information regarding study conduct and progress will be reported to the Institutional Review Board (IRB) and Data and Safety Monitory Board (DSMB) per current institutional standards. The trial will not be initiated until there is approval by the IRB of the protocol. The IRB should be duly constituted according to regulatory requirements. The investigator will inform the IRB of the progress of the trial at least yearly. Any changes to the protocol will be made in the form of a written amendment and must be approved by the IRB prior to implementation. Protocol changes to eliminate an immediate hazard to a trial patient may be implemented by the investigator immediately. The investigator must then immediately inform the IRB and DSMB.

# **Good Clinical Practice**

This study will be carried out in compliance with the protocol and Good Clinical Practice (GCP), as described within:

- 1. ICH Harmonized Tripartite Guidelines for Good Clinical Practice 1996.
- Declaration of Helsinki, concerning medical research in humans (Recommendations Guiding Physicians in Biomedical Research Involving Human Subjects, Helsinki 1964, amended Tokyo 1975, Venice 1983, Hong Kong 1989, Somerset West 1996).

The investigator agrees to adhere to the instructions and procedures described within the above and thereby to adhere to the principles of Good Clinical Practice with which the above conform.

#### Confidentiality

It is the responsibility of the investigator to ensure the confidentiality of patients participating in the trial. Case report forms (CRFs) and other documents submitted to regulatory authorities must not contain the name of a trial patient. All patients in the trial will be identified by a unique identifier which will be used on all CRFs, and any other material submitted to regulatory authorities. All case report forms, and any identifying information must be kept in a secure location with access limited to the study staff directly assisting with the trial.

#### **Study Termination**

Reasons for study termination may include, but are not limited to, the following:

- 1. Investigator non-compliance with the protocol, GCP or regulatory requirements
- 2. Insufficient enrollment
- 3. Safety concerns
- 4. Decision by suppliers to modify or discontinue the availability, development or manufacture of protocol-indicated treatment or device
- 5. A request to discontinue the study by the IRB or a recognized regulatory authority

#### **Benefits, Compensation and Additional Costs**

There will be no financial compensation for participation. There is no additional benefit to the patient by participating the in the trial. Data from this study will be beneficial to the field. There will be no additional cost to subjects for participating in this study. Subjects and/or their insurance companies will be responsible for all care provided as part of the procedure as this service is part of the standard of care they would receive for their condition.

# STUDY COORDINATION

#### **Trial Compliance**

This is an investigator-initiated study. The Principal Investigator, [name]. is conducting the study and Vanderbilt University Medical Center (VUMC) will act as the sponsor.

#### **Protocol Deviations**

Vanderbilt University Medical Center is responsible for implementing and maintaining quality assurance and quality control to ensure that studies are conducted according to the protocol, GCP, and all applicable regulatory requirements. A protocol deviation is any noncompliance with the protocol. Noncompliance can be on the part of the study participant, the investigator, or the study site staff. Deviations to the protocol are not permitted except when necessary to eliminate an immediate hazard to study subjects.

#### **Record Retention**

An electronic case report form (eCRF) is required and must be completed for each included participant. Records will be retained compliant with institutional, federal, and local regulations. Secondary use of the data will be with IRB approval. The dataset may be made available outside of the study team on reasonable request with approval from an authorized Institutional Review Board and concurrence with the study team that the data are fit for purpose.

# PLANS FOR DISSEMINATION OF FINDINGS

Any manuscript or releases resulting from the collaborative research must be approved by the investigator and will be circulated to applicable participating investigators prior to submission for publication or presentation. A publication plan consistent with the international Committee of Medical Journal Editors (ICMJE) will be created prior to analysis and publication of any data. All data will be made available to authors as required. The publication of sub-studies and post-hoc analyses will not precede the primary publication. Publication of results will be determined by the investigators. All authors are expected to disclose financial or affiliations that could be considered conflicts of interest per journal or medical society requirements.

Official Title: Robotic versus Electromagnetic Bronchoscopy for Pulmonary LesIon AssessmeNT: the RELIANT trial.

NCT Number: NCT05705544

Date: March 18, 2024

Statistical analysis plan for Robotic versus Electromagnetic Bronchoscopy for Pulmonary LesIon AssessmeNT: the RELIANT trial PI: [name]

Robotic versus Electromagnetic Bronchoscopy for Pulmonary LesIon AssessmeNT: the **RELIANT** trial

Statistical Analysis Plan

[name]

[name] – Current Lead Biostatistician

[name] – Current Lead Biostatistician

[name]

[name]

[name] – Current Lead Biostatistician

[name]

[name] – Current Lead Biostatistician

not ll

[name] – Initial Lead Biostatistician

Change in Lead Biostatisticians occurred due to [name] departure from VUMC on 12/31/2022.

Date

January 11, 2023 Date

July 12, 2022 Date

Page 1

August 15, 2023

09/28/2023

Date

Date

3/18/2024

Statistical analysis plan for Robotic versus Electromagnetic Bronchoscopy for Pulmonary LesIon AssessmeNT: the RELIANT trial

PI: [name]

Introduction

Advanced imaging and navigational guidance systems are often used to sample peripheral lung lesions. Electromagnetic navigation bronchoscopy (EMN) and shape-sensing catheter bronchoscopy (SSCB) are the most commonly used modalities. These devices are considered equivalent, usual care options for sampling peripheral pulmonary lesions, with similar side effect profiles. Despite EMN and SSCB being routinely used in clinical care there is no randomized data directly comparing these two platforms. This document describes the statistical analysis plan for a single center, open label, pragmatic, non-inferiority, cluster randomized controlled trial designed to evaluate the impact of these two platforms for improving clinical care for patients with peripheral lung lesions. This document has been prepared prior to final data collection and unblinding. It is hypothesized that the diagnostic yield of the IonTM Endoluminal System (SSCB) is not inferior to the ILLUMISITETM Platform (EMN) in patients undergoing bronchoscopy to biopsy a peripheral lung lesion (PPL).

Population and design considerations

Study Population:

Patients who are undergoing a navigational bronchoscopy for biopsy of a peripheral lung lesion and are ≥ 18 years of age at the time of the procedure will be included in this study. Patients will be excluded if they are enrolled in a different study requiring use of one of these specific platforms or if they decline to participate.

Study Design:

This is a single center, open label, pragmatic, non-inferiority, cluster randomized controlled trial comparing clinical outcomes between patients assigned to receive a diagnostic bronchoscopy with either the IonTM Endoluminal System (SSCB) or the ILLUMISITETM Platform (EMN) platform.

Randomization:

Operating rooms are set up each morning with one of the two devices for the day's of prescheduled procedures. Cluster randomization will be used for this study given impracticability of patient-level 1:1 parallel randomization in these circumstances. The ILLUMISITETM Platform (EMN) and IonTM Endoluminal System (SSCB) will be randomly allocated to our two operating rooms each day. All patients undergoing a navigational bronchoscopy will have their procedure performed with the platform assigned to their operating room for the day. A biostatistician not involved in patient care will generate the randomization sequence. Random permuted blocks may be used to ensure balanced cluster allocation. A bronchoscopy scheduler with no knowledge of the allocation scheme will schedule each patient into one of the two operating rooms. Allocations will be concealed in sealed envelopes which will be opened every morning by the operating room staff preparing the rooms.

Sample Size Considerations:

The study team performs 1-4 guided bronchoscopies per day (average of 2 per day) and approximately 400 per year. Based on data from prior studies and the study team's published data, we estimated the diagnostic yield of EMN to be 80%. The diagnostic yield of SSCB has not been fully elucidated, but published data suggest an overall diagnostic yield of 80% as well. Assuming the diagnostic yield for the ILLUMISITE[™] Platform (EMN) is 80%, with a non-

Statistical analysis plan for Robotic versus Electromagnetic Bronchoscopy for Pulmonary LesIon AssessmeNT: the RELIANT trial

PI: [name]

inferiority margin set at 10%, cluster size of 2, and no intracluster correlation, we need 202 clusters (operating days) to have an 80% power to conclude noninferiority at a one-sided type I error rate of 5%, which corresponds to a target of 425 subjects to reach 202 per arm. The noninferiority margin has been chosen based on what would be considered a clinically significant difference (or, put differently, a difference which might influence a hospital to purchase one platform over the other). In case our average cluster size does not reach 2, we will plan to increase the number of clusters to meet our target enrollment of 425 subjects to reach 202 per arm.

Interventions

All patients meeting the eligibility criteria for this study will be enrolled. Cluster randomization will be used, and patients will be assigned to one of the two comparator arms:

a) IonTM Endoluminal System (SSCB)

b) ILLUMISITE[™] Platform (EMN)

Outcomes

Primary Outcome

The primary endpoint will be diagnostic yield, defined as the proportion of procedures that results in acquisition of lesional tissue.

Lesional tissue is defined by the presence of pathological findings that readily explain the presence of a pulmonary lesion. The following common pathological findings are pre-specified:

- Malignancy
- Specific benign pathologic finding including
 - Organizing pneumonia
 - Frank purulence/robust neutrophilic inflammation
 - o Granulomatous inflammation
 - Other specific benign findings such as hamartoma, amyloidoma or other uncommon causes of PPLs with distinctive pathological patterns.

Biopsies not meeting any of the above lesional pathological criteria will be adjudicated as not meeting the primary outcome (not being "diagnostic"), including biopsies with normal lung parenchyma or airway components on biopsy, atypia not diagnostic of malignancy, or non-specific inflammation. A blinded panel will review all non-malignant biopsies at the end of accrual to confirm specific benign or non-diagnostic findings on biopsy. Procedures will be adjudicated as not meeting the primary outcome if the procedure starts but biopsies are not obtained (due to failure to navigate to the lesion, or complication, or equipment failure). A procedure will be considered started at induction of general anesthesia.

Statistical analysis plan for Robotic versus Electromagnetic Bronchoscopy for Pulmonary LesIon AssessmeNT: the RELIANT trial PI: [name]

Biopsies obtained without the use of EMN or SSCB (e.g., sampling of central lymph nodes using the linear endobronchial ultrasound bronchoscope) will not be included in the diagnostic yield calculations. In case of repeat bronchoscopies, only the index bronchoscopy will be included in the diagnostic yield calculation.

Secondary Outcomes

There is one secondary outcome for the trial, which will be collected during the bronchoscopy procedure.

a) Duration of procedure (in minutes), defined as time from the start of airway registration to

the removal of the bronchoscope after completion of navigation procedures.

Exploratory Endpoint(s)

There are three exploratory endpoints that are prespecified. These can be collected during and immediately after the bronchoscopy procedure, and/or during the follow-up period.

a) Need for additional diagnostic procedures. Any diagnostic procedure performed within 12 months of the study bronchoscopy that targets the same peripheral lesion (including repeat bronchoscopy, transthoracic needle biopsy, or surgical lung biopsy) will be considered an additional diagnostic procedure.

1. Repeat biopsies of lesions determined to be malignant by study bronchoscopy which are 1) performed specifically to obtain additional tissue for further testing but that does not change the malignant diagnosis, or 2) therapeutic surgical resection of such lesions, will not be considered additional diagnostic procedures.

b) Radiation exposure, defined as radiation dose delivered to the patient during the study bronchoscopy, recorded as a dose area product (mGy/cm2).

Diagnostic accuracy

Diagnostic accuracy will be assessed for the two devices. Lesions will be categorized as positive (malignant) lesions or negative (specific benign diagnosis). The criterion standard for a negative diagnosis will be no evidence of malignancy at 12-month follow-up (no interval biopsy diagnostic of malignancy, regression on CT or stable size with no plan for repeat diagnostic procedure).

Safety outcome

The main safety outcome for this trial is occurrence of procedure complication(s), defined as the occurrence of any of the following: respiratory failure, pneumothorax, anesthetic complications, and bronchopulmonary hemorrhage.

Safety outcomes will be reported overall and by type.

Statistical analysis plan for **R**obotic versus Electromagnetic Bronchoscopy for Pulmonary LesIon Assessme**NT**: the RELIANT trial PI: [name]

Analysis dataset

The analysis for the trial will use a intent-to-treat approach. Participants will be evaluated by treatment group as assigned regardless of what was delivered; participants will be excluded if their procedure did not begin, defined as the start of the navigation procedure itself. All eligible participants will be included.

The safety analysis dataset will group participants by device used, regardless of assignment.

Statistical Approach

Our initial analysis will be descriptive in nature, summarizing information that characterizes the cohort and the outcomes. Then, we will proceed with inferential analysis. No interim analyses are planned.

Descriptive Analysis

To characterize the study sample, baseline demographic and clinical data will be described overall and by group. Categorical variables will be described using frequencies and proportions, and continuous variables will be described using means and standard deviations or medians and interquartile ranges, as appropriate. Missingness will be reported for each variable. At a minimum, the following variables will be described at time of enrollment:

- Age (years)
- Gender (male, female, unknown)
- Race (African American, Asian/Pacific Islander, Caucasian, Multiple, Native American, Other, Unknown)
- Ethnicity (Hispanic, Non-Hispanic, Unknown)
- History of cancer (yes/no)
- Smoking History (current, former, never)
- Body mass index (BMI)
- Lesion characteristics
 - o Size (mm)
 - Location (middle vs peripheral)
 - Upper lobe (yes/no)
 - Density (solid, part solid, ground glass opacity)
 - Distance from pleura (cm)
 - Bronchus sign present (yes/no)
- Procedure details

Statistical analysis plan for **R**obotic versus Electromagnetic Bronchoscopy for Pulmonary LesIon AssessmeNT: the RELIANT trial PI: [name]

PI: [name]

- Rapid onsite evaluation (yes/no)
- o Operator
- Digital tomosynthesis (yes/no)
- Cone beam computed tomography (yes/no)
- Biopsy tools

We will describe the outcome variables overall and grouped by study arm using the same approach as for the demographic data. Summary statistics and graphical representations may be displayed, and missingness will be reported for each variable. No statistical comparisons between groups will be done for this descriptive analysis.

Primary analysis

The primary analysis for the trial will use an intent-to-treat approach. Participants will be evaluated by treatment group as assigned regardless of what was delivered. All eligible participants will be included.

The primary outcome variable (diagnostic yield) will be compared between groups using a generalized linear mixed model with one-sided test. The primary model will be covariate adjusted, including fixed effects for device assignment, lesion size, density, peripheral location, and bronchus sign, and a random effect for operator. Should the model demonstrate signs of overfitting, covariates may be selected based on priority order (device assignment, lesion size, density, peripheral location, sign, operator).

If non-inferiority is demonstrated, we will proceed with a superiority analysis using the same approach as the non-inferiority analysis, an adjusted generalized linear mixed effects model with the same covariates used in the primary analysis. No adjustment will be made for multiplicity. The superiority analysis would be conducted at a one sided p-value of 0.05.

Secondary and exploratory analysis

A sensitivity analysis using a *per protocol* approach will be conducted to analyze participants based on the device used. We will use the same approach as the primary analysis, an adjusted generalized linear mixed effects model using the same covariates.

The secondary outcome, procedure duration, will be compared between study groups using a linear mixed model. If the procedure duration is skewed, alternative models may be pursued,

Statistical analysis plan for **R**obotic versus Electromagnetic Bronchoscopy for Pulmonary LesIon AssessmeNT: the RELIANT trial PI: [name] such as a cox regression. The primary model will be covariate adjusted following a similar approach to the analysis of the primary outcome. Analysis of the exploratory endpoints will follow a similar approach.

Safety analysis

Procedure complications are expected in usual care, although uncommon. We will report all procedure complications for each device, overall and by type. If event rates exceed 5%, we may proceed with a comparative analysis, which will involve a generalized linear mixed regression model for binary outcomes as specified for the main analysis, with the exception that covariate adjustment may not be possible. The safety analysis dataset will group participants by device used, regardless of assignment.

All model results will be summarized with point estimates and 95% confidence intervals (CIs), which will be emphasized over p-values when reporting the results for secondary outcomes. No adjustments for multiplicity will be made.

Differential effects

To determine whether differences in outcomes are dependent on baseline characteristics, we will introduce interaction terms into the models developed for the main analysis. Specifically, we will test the interaction between device assignment and the subgrouping variable. Each variable will be tested one by one, such that all main effects but only one interaction term is included at a time. The following putative subgrouping variables are prespecified:

- Nodule size (continuous, treatment effects will be estimated at 1.5cm and 3cm)
- Presence of bronchus sign
- Solid vs subsolid nodule
- Peripheral vs central location Peripheral defined as outer 1/3 of chest

Missingness on the primary or secondary outcome is not expected due to the proximity of its measurement with the procedure and its integration into clinical documentation. Procedures missing the primary outcomes will be considered not diagnostic. Missing covariates will be imputed using multiple imputation with predictive mean matching. There may be missingness on exploratory outcomes. For missing exploratory outcomes, a complete case analysis will be performed.

Statistical analysis plan for Robotic versus Electromagnetic Bronchoscopy for Pulmonary LesIon AssessmeNT: the RELIANT trial

PI: [name]

Diagnostic accuracy

Diagnostic test statistics (e.g., sensitivity, specificity, predictive values, likelihood ratios) will be reported for the two devices. In addition, accuracy of the diagnosis may be modeled using a generalized linear model to explore whether participant or lesion features are predictive of procedure success, as described for the differential effects analysis.

Summary

The results of this study will help to determine whether there is a difference between these two diagnostic bronchoscopy platforms for patient outcomes. The analysis approach we describe is selected based on the trial's pragmatic nature and specifically the intent to understand if the diagnostic yield of the IonTM Endoluminal System (SSCB) is not inferior to the ILLUMISITETM Platform (EMN) in patients undergoing bronchoscopy to biopsy a peripheral lung lesion.

Version and Revision Log

7/12/2022	Version 1: developed with and approved by [name].
1/11/2023	Version 1: [name] departed VUMC and [name] became the current lead biostatistician and reviewed and approved the SAP.
8/14/2023	 Version 2: Edits developed with and approved by [name] Revisions: Adding the exclusion criterion that subjects can decline to participate. Minor clarifications to the primary, secondary, and safety
	 outcomes. Adjustments to the analysis, differential effects, and missingness sections to be in alignment with the protocol manuscript.
9/28/2023	 Version 3: Edits developed with and approved by [name] Revisions: Clarifying the anticipated number of patients and clusters to be enrolled for this study.
3/18/2024	 Version 4: Edits developed with and approved by [name] Revisions: Clarifying the anticipated number of patients to ensure 202 patients will be enrolled per arm.

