# **Outcomes Definitions**

- *Rate of complications:* Number of procedures resulting in any complication divided by the total number of procedures.
- *Rate of specific complication:* Number of procedures resulting in a specific complication divided by the total number of procedures.
- *Need for additional diagnostic procedures:* Any diagnostic procedure performed after the study bronchoscopy which targets the same peripheral lesion (including repeat bronchoscopy, transthoracic needle biopsy, or surgical lung biopsy) will be considered an additional diagnostic procedure. Repeat biopsies of lesions determined to be malignant by study bronchoscopy which are 1) performed specifically to obtain additional tissue for further testing but that does not change the malignant diagnostic, or 2) therapeutic surgical resection of such lesions, will not be considered additional diagnostic procedures.
- *Radiation exposure:* Radiation dose delivered to the patient during the study bronchoscopy, recorded as a dose area product (mGy/cm2).
- *Diagnostic accuracy:* Number of true positive (malignant) lesions plus true negative (specific benign diagnosis) lesions with no evidence of malignancy at 12-month follow-up (no interval biopsy diagnostic of malignancy, regression on CT or stable size with no plan for repeat diagnostic procedure), divided by the total number of biopsied lesions.

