Patients not diagnosed with malignancy following bronchoscopic biopsy will be followed clinically per standard of care. We will review their interval chest CT scans to assess the target lesion for progression, regression, or stability for up to 12 months. If any additional biopsies of the target lesion are obtained by alternative means (transthoracic needle biopsy, surgical biopsy), definitive pathological results as previously defined will be compared to the bronchoscopy biopsies.

Study Procedures	Day 1	Within 7 Days	3 Month	6 Months	12 Months
Inclusion/exclusion criteria	X				
Randomization	Х				
Clinical and demographic data	Х				
Adverse events	Х	Х			
Pathology review		Х			
Chest CT	Per SOC		Per SOC	Per SOC	Per SOC
Bronchoscopy	Per SOC				
Follow-up			Per SOC	Per SOC	Per SOC

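### The true-negative rule for 12-month diagnostic accuracy ignores interval cancer treatment, so a treated lesion that shrinks or stays stable counts as verified benign

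*SAP*

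**What the plan says.** Diagnostic accuracy is listed among the exploratory outcomes in both documents. Under Outcomes Definitions, the Protocol counts malignant lesions as true positives, adds "true negative (specific benign diagnosis) lesions with no evidence of malignancy at 12-month follow-up", and takes the sum "divided by the total number of biopsied lesions". The SAP section on diagnostic accuracy (under Outcomes) says "The criterion standard for a negative diagnosis will be no evidence of malignancy at 12-month follow-up", and both documents explain that phrase with the same bracket: "no interval biopsy diagnostic of malignancy, regression on CT or stable size with no plan for repeat diagnostic procedure".

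The bracket uses three kinds of information: tissue from a later biopsy, change on CT, and whether a repeat diagnostic procedure is planned. Treatment is not among them.

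The follow-up in Protocol, Study Procedures matches this. For patients without a cancer diagnosis, "We will review their interval chest CT scans to assess the target lesion for progression, regression, or stability for up to 12 months", with imaging per standard of care, and pathology from any further biopsy of the target is compared with the index result. The minimum variable list in SAP, Descriptive Analysis records history of cancer at enrollment and no treatment after the biopsy.

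**The concern.** Shrinkage or stability on CT supports a benign diagnosis only if nothing was done in the interval that would shrink or hold a cancer. Local treatment given on clinical suspicion, or systemic therapy for a known cancer elsewhere, breaks that link. The CT course then no longer separates a benign lesion from a treated malignant one.

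The final SAP section on diagnostic accuracy commits to sensitivity, specificity, predictive values and likelihood ratios for each device. Among biopsy-negative lesions, this one rule separates true from false negatives. Any missed cancer that passes the rule moves from the false-negative to the true-negative cell, so the error runs in one direction: negative predictive value (NPV), sensitivity and accuracy all rise.

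**Working it through.** **Plan's own figures.** The documents state no figure for diagnostic accuracy. The one design figure, power 0.80327 with 202 per arm, reproduces with the Farrington-Manning score test (80% in both arms, margin 10%, one-sided 5%, no intracluster correlation). It plays no part in this point.

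**Logical check.** Take a lesion whose index biopsy shows a specific benign finding but which is a cancer. It receives cancer-directed treatment without further tissue, or the patient receives systemic cancer therapy, and the lesion then regresses or stays stable. Apply the bracket on its strictest reading, with all conditions required:

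| Condition | Result |
|---|---|
| No malignant interval biopsy | Met: no biopsy was taken |
| Regression or stable size on CT | Met: a plausible result of treatment |
| No plan for a repeat diagnostic procedure | Met: none planned |

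The lesion is a true negative even on the strict reading, so the conclusion does not depend on how the list is punctuated.

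**Search for a safeguard.** No other section closes the gap. The blinded panel (Protocol, Primary Outcome) confirms biopsy findings at the end of accrual; it is not asked to judge 12-month status. The rule on therapeutic resection sits under additional diagnostic procedures and concerns only lesions already found malignant.

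**Size per lesion.** Assume one lesion per patient and 202 per arm. Each affected lesion shifts accuracy by 1/202 = 0.5 percentage point.

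**Illustration.** The documents give none of the rates, so these inputs are assumptions. Take 40 specific benign results per arm (about 20% of 202), of which 3 are cancers. With 80% yield, 0.80 × 202 ≈ 162 are diagnostic, which leaves 162 − 40 = 122 malignant. Let m be the number of the 3 missed cancers that pass the stated rule because they were treated without tissue.

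| m | NPV = (37+m)/40 | Sensitivity = 122/(125−m) | Accuracy = (159+m)/202 |
|---|---|---|---|
| 0 | 92.5% | 97.6% | 78.7% |
| 1 | 95.0% | 98.4% | 79.2% |
| 2 | 97.5% | 99.2% | 79.7% |

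The first row is the correct classification. Sensitivity here counts only missed cancers among specific benign results.

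**Wider range.** Let b be the share of lesions with a specific benign result and f the share of those that are missed cancers treated without tissue. The overstatement of accuracy is b × f. With f = 0 it is zero. With b = 15%, f = 2% it is 0.3 point (202 × 0.15 × 0.02 = 0.6 lesion). With b = 35%, f = 10% it is 3.5 points (202 × 0.35 × 0.10 = 7.1 lesions).

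**The case against.** The strongest reply is that the governing phrase, absence of evidence of malignancy at 12 months, does the work and the bracket only illustrates it. A lesion treated as presumed cancer has a clinical judgement of malignancy in the chart, so an assessor could decline to call it a true negative. That is a fair reading, but the bracket does not say so, and the documents name no blinded assessor for 12-month status in an open-label trial. The phrase also does not reach systemic therapy given for another cancer, where nobody has judged the target lesion malignant.

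Second, the affected case is narrow. It needs a specific benign finding confirmed by the panel, treatment without tissue, and regression or stability. Resection would normally give pathology and be caught. This stands: the count may be very small or zero.

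Third, the minimum variable list does not show that treatment data are unavailable. This also stands. Protocol, Data Collection provides for chart abstraction and access to clinical notes, medication data and reimbursement codes. What is missing is the rule that uses them.

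Fourth, scoring every treated lesion as cancer would create the opposite error, since some lesions treated on suspicion are benign. This stands and shapes the fix.

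**Conclusion.** The point holds as a gap in the definition of an exploratory endpoint. The stated rule classes a treated, unverified lesion as a verified benign one, and nothing elsewhere corrects it. NPV, sensitivity and accuracy can be inflated; accuracy by about 0.5 point per affected lesion, assuming 202 lesions per arm. The number of such lesions is unknown and may be zero. Diagnostic yield, the non-inferiority test and the sample size are unaffected.

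Four stronger readings are tempting, but the documents do not support them:

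- **An enlarging lesion that is never re-biopsied would qualify.** This needs the bracket to be three free-standing alternatives, which conflicts with the governing phrase and makes the CT terms pointless. It warrants only making the joint reading explicit.
- **Non-diagnostic biopsies enlarge the problem.** The SAP states "Lesions will be categorized as positive (malignant) lesions or negative (specific benign diagnosis". Atypia, non-specific inflammation and normal tissue are non-diagnostic and cannot be true negatives.
- **Regression under treatment points to malignancy.** An organizing pneumonia or an infection can also resolve in a patient treated for another cancer. The regression is uninformative.
- **The comparison between devices is biased.** That would follow only if such cases differed by arm, and the documents give no figure or mechanism for a difference.

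**What to change.** In Protocol, Outcomes Definitions, and in the SAP outcome section on diagnostic accuracy, state that a true negative is a specific benign index biopsy with all of the following, joined by AND:

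1. no malignant tissue result in the interval;
2. regression or stability on the last available CT within the 12-month follow-up, with no plan for a repeat diagnostic procedure;
3. no cancer-directed treatment between the index biopsy and that CT, whether local or systemic therapy able to affect the lesion.

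The last available CT is used because imaging follows standard of care for up to 12 months; a scan required at exactly 12 months would discard lesions that resolved earlier.

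Abstract interval treatment from the chart. Class treated lesions without tissue as indeterminate in the main accuracy analysis. In a sensitivity analysis, count those treated as presumed cancer as reference-positive; lesions exposed only to systemic therapy for another cancer stay indeterminate.

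State how indeterminate lesions enter each statistic. Under the Protocol's denominator of all biopsied lesions, they stay in the denominator of accuracy but not in its numerator. If they are removed from the NPV calculation, NPV barely moves: in the illustration with m = 2 it is 37/38 = 97.4%, against 39/40 = 97.5% under the stated rule, whereas counting both as reference-positive gives 37/40 = 92.5%. So report the number of indeterminate lesions per arm and show both analyses together.

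The cost is a short amendment to each document, one abstracted field and slightly fewer verified negatives. The rule concerns outcome classification only and directs no care. It should be fixed before 12-month status is classified.
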